5. INTERIM ANALYSES

An interim analysis was planned for Japanese patients when the final Japanese patient completes his/her EOT visit. The analysis details were prepared in a separate interim analysis plan.

6. CHANGES OF ANALYSIS FROM PROTOCOL

Not applicable.

8. APPENDICES

8.1 Appendix A Analysis visit windows

Table 2 Adjusted visit windows for variables with scheduled visits every 4 weeks (eg, EQ-5D-5L)

| Analysis Visit | Scheduled study day | Adjusted visit window |
|--------------------------|---------------------|----------------------------------|
| Week 0 | 1 | Study Day \leq 1 |
| Week 4 | 29 | 2 \leq Study Days \leq 42 |
| Week 8 | 57 | 43 \leq Study Days \leq 70 |
| Week 12 | 85 | 71 \leq Study Days \leq 98 |
| Week 16 | 113 | 99 \leq Study Days \leq 126 |
| Week 20 | 141 | 127 \leq Study Days \leq 154 |
| Week 24 | 169 | 155 \leq Study Days \leq 182 |
| Week 28 | 197 | 183 \leq Study Days \leq 210 |
| Week 32 | 225 | 211 \leq Study Days \leq 238 |
| Week 36 | 253 | 239 \leq Study Days \leq 266 |
| Week 40 | 281 | 267 \leq Study Days \leq 294 |
| Week 44 | 309 | 295 \leq Study Days \leq 322 |
| Week 48 | 337 | 323 \leq Study Days \leq 350 |
| Week 52 | 365 | 351 \leq Study Days \leq 378 |
| Week 56 (EOT for adults) | 393 | 379 \leq Study Days \leq 406 |
| Week 68# (FU for adults) | 477 | 407 \leq Study Days |
| Week 60* | 421 | 407 \leq Study Days \leq 434 |
| Week 64* | 449 | 435 \leq Study Days \leq 462 |
| Week 68* | 477 | 463 \leq Study Days \leq 490 |
| Week 72* | 505 | 491 \leq Study Days \leq 518 |
| Week 76* | 533 | 519 \leq Study Days \leq 546 |
| Week 80* | 561 | 547 \leq Study Days \leq 574 |
| Week 84* | 589 | 575 \leq Study Days \leq 602 |
| Week 88* | 617 | 603 \leq Study Days \leq 630 |
| Week 92* | 645 | 631 \leq Study Days \leq 658 |
| Week 96* | 673 | 659 \leq Study Days \leq 686 |
| Week 100* | 701 | 687 \leq Study Days \leq 714 |

Table 2 Adjusted visit windows for variables with scheduled visits every 4 weeks (eg, EQ-5D-5L)

| Analysis Visit | Scheduled study day | Adjusted visit window |
|---------------------------------|---------------------|-----------------------|
| Week 104* | 729 | 715≤Study Days≤742 |
| Week 108* (EOT for adolescents) | 757 | 743≤Study Days≤770 |
| Week 120* (FU for adolescents) | 841 | 771≤Study Days |

Visit for adults only.

* Visits for adolescents only.

Table 3 Adjusted visit windows for variables with scheduled every 12 weeks visits (eg, ACQ-6 and AQLQ(S)+12)

| Analysis Visit | Scheduled study day | Adjusted visit window |
|---------------------------------|---------------------|-----------------------|
| Week 0 | 1 | Study Day≤1 |
| Week 12 | 85 | 2≤Study Days≤126 |
| Week 24 | 169 | 127≤Study Days≤210 |
| Week 36 | 253 | 211≤Study Days≤294 |
| Week 48 | 337 | 295≤Study Days≤378 |
| Week 56# (EOT for adults) | 393 | 379≤Study Days≤434 |
| Week 68# (FU for adults) | 477 | 435≤Study Days |
| Week 60* | 421 | 379≤Study Days≤462 |
| Week 72* | 505 | 463≤Study Days≤546 |
| Week 84* | 589 | 547≤Study Days≤630 |
| Week 96* | 673 | 631≤Study Days≤714 |
| Week 108* (EOT for adolescents) | 757 | 715≤Study Days≤798 |
| Week 120* (FU for adolescents) | 841 | 799≤Study Days |

Visit for adult only.

* Visits for adolescents only.

Table 4a Adjusted visit windows for hematology, cell marker, immunology, microbiology tests

| Analysis Visit | Scheduled study day | Adjusted visit window |
|---------------------------------|---------------------|----------------------------------|
| Week 0 | 1 | Study Day \leq 1 |
| Week 12 | 85 | 2 \leq Study Days \leq 140 |
| Week 28 | 197 | 141 \leq Study Days \leq 252 |
| Week 44 | 309 | 253 \leq Study Days \leq 350 |
| Week 56 (EOT for adults) | 393 | 351 \leq Study Days \leq 462 |
| Week 68# (FU for adults) | 477 | 463 \leq Study Days |
| Week 76* | 533 | 463 \leq Study Days \leq 588 |
| Week 92* | 645 | 589 \leq Study Days \leq 700 |
| Week 108* (EOT for adolescents) | 757 | 701 \leq Study Days \leq 798 |
| Week 120* (FU for adolescents) | 841 | 799 \leq Study Days |

Visit for adult only.

* Visits for adolescents only.

Table 5b Adjusted visit windows for Chemistry laboratory tests - part 1

| Analysis Visit | Scheduled study day | Adjusted visit window |
|---------------------------------|---------------------|----------------------------------|
| Week 0 | 1 | Study Day \leq 1 |
| Week 12 | 85 | 2 \leq Study Days \leq 140 |
| Week 28 | 197 | 141 \leq Study Days \leq 252 |
| Week 44 | 309 | 253 \leq Study Days \leq 350 |
| Week 56 (EOT for adults) | 393 | 351 \leq Study Days |
| Week 56 (For adolescents) | 393 | 351 \leq Study Days \leq 462 |
| Week 76* | 533 | 463 \leq Study Days \leq 588 |
| Week 92* | 645 | 589 \leq Study Days \leq 700 |
| Week 108* (EOT for adolescents) | 757 | 701 \leq Study Days |

Apply for chemistry (excluding tests: Calcium, Chloride, CO₂, Glucose, Phosphorus, Potassium, Sodium, Total cholesterol and Uric acid) and Urine tests.

Visit for adult only.

* Visits for adolescents only.

Table 6c Adjusted visit windows for chemistry laboratory tests - part2

| Analysis Visit | Scheduled study day | Adjusted visit window |
|---------------------------------|----------------------------|----------------------------------|
| Week 0 | 1 | Study Day \leq 1 |
| Week 12 | 85 | 2 \leq Study Days \leq 238 |
| Week 56 (EOT for adults) | 393 | 239 \leq Study Days \leq 574 |
| Week 108* (EOT for adolescents) | 757 | 575 \leq Study Days |

For chemistry labs: Calcium, Chloride, CO₂, Glucose, Phosphorus, Potassium, Sodium, Total cholesterol and Uric acid.

* Visits for adolescents only.

Table 7 Adjusted visit windows for PK (unscheduled samples only) and ADA (including nAb)

| Analysis Visit | Scheduled study day | Adjusted visit window |
|---------------------------------|----------------------------|----------------------------------|
| Week 0 | 1 | Study Day \leq 1 |
| Week 8 | 57 | 2 \leq Study Days \leq 84 |
| Week 16 | 113 | 85 \leq Study Days \leq 154 |
| Week 28 | 197 | 155 \leq Study Days \leq 252 |
| Week 44 | 309 | 253 \leq Study Days \leq 336 |
| Week 52 | 365 | 337 \leq Study Days \leq 385 |
| Week 56# (EOT for adults) | 393 | 386 \leq Study Days \leq 434 |
| Week 68# (FU for adults) | 477 | 435 \leq Study Days |
| Week 60* | 421 | 386 \leq Study Days \leq 476 |
| Week 76* | 533 | 477 \leq Study Days \leq 588 |
| Week 92* | 645 | 589 \leq Study Days \leq 700 |
| Week 108* (EOT for adolescents) | 757 | 701 \leq Study Days \leq 798 |
| Week 120* (FU for adolescents) | 841 | 799 \leq Study Days |

Visit for adult only.

* Visits for adolescents only.

Note that the Week 52 window has a shorter window range (3 weeks) post scheduled study day due to adjustment for adult group having a scheduled EOT visit 4 weeks later.

Table 8 Adjusted visit windows for Pre-BD spirometry

| Analysis Visit | Scheduled study day | Adjusted visit window |
|---------------------------------|---------------------|----------------------------------|
| Week 0 | 1 | Study Day \leq 1 |
| Week 16 | 113 | 2 \leq Study Days \leq 168 |
| Week 32 | 225 | 169 \leq Study Days \leq 280 |
| Week 48 | 337 | 281 \leq Study Days \leq 385 |
| Week 56# (EOT for adults) | 393 | 386 \leq Study Days |
| Week 64* | 449 | 386 \leq Study Days \leq 504 |
| Week 80* | 561 | 505 \leq Study Days \leq 616 |
| Week 96* | 673 | 617 \leq Study Days \leq 728 |
| Week 108* (EOT for adolescents) | 757 | 729 \leq Study Days |

Visit for adult only.

* Visits for adolescents only.

Note that Week 48 window has shorter window range (7 weeks) post scheduled study day due to adjustment for adult group having a scheduled EOT visit 8 weeks later.

8.2 Appendix B Partial and missing date imputation

Dates missing the day or both the day and month of the year will adhere to the following conventions in order to classify on-treatment AEs and to classify prior/concomitant medications.

For AE start date or medication start date:

Partial missing start date:

- Missing day of the month: 1st day of the month
- Missing day and month: Jan. 1st of the year

Completely missing start date:

- If AE end date or medication end date is missing, then impute the start date as the first visit date (Visit 1)
- If AE end date or medication end date is before the first visit date (Visit 1), then impute the start date as the end date
- If AE end date or medication end date is after the first visit date (Visit 1), then impute the start date as the first visit date (Visit 1)
- Otherwise, impute the start date as the first visit date (Visit 1)

For AE end date or medication end date:

Partial missing end date:

- Missing day of the month: Last day of the month
- Missing day and month: Dec. 31st of the year
- Further adjust by selecting the earlier of the imputed date, death date, and post-treatment end date*.

Post-treatment end date* is defined as the last visit date or the discontinuation of study day, whichever is later.

Completely missing end date:

- AE end date will be left as missing
- Medication end date will be imputed as earlier of death date and post-treatment end date (as defined above).

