3.1.1 Adverse events

Adverse event (AE) and serious adverse event (SAE) are defined in Section 7.1 of the CSP. All AEs, including SAEs, will be collected from the time the patient signs the informed consent throughout the treatment period and including the follow-up period (Visit 16, Week 68 for adults, and Visit 29, Week 120 for adolescents). Any AEs that are unresolved at follow-up in the study will be followed up by the Investigator for as long as medically indicated, but without further recording in the CRF. If the record was entered in CRF for an ongoing event post-study follow-up visit, study output will list those events and indicates as such.

Adverse events experienced by the patients will be collected throughout the entire study and will be coded by the AstraZeneca designee using the latest version of the Medical Dictionary for Regulatory Activities (MedDRA).

Adverse event data will be categorised according to their onset date into the following study periods:

- AEs in the on-study period are defined as those with onset between the day of first dose of study treatment and the day of the scheduled follow-up visit, inclusive.
- AEs in the on-treatment period are defined as those with onset between the day of the first dose of study treatment and scheduled EOT for patients who complete study treatment or scheduled IPD visit for those patients who prematurely discontinue study treatment, inclusive. If the EOT or IPD visit is beyond the protocol defined visit window, AEs with onset after the day of last dose of study treatment date + 28 days + 7 days (visit window) will be excluded from the on-treatment period and instead assigned to the post-treatment period.
- AEs in the post-treatment period are defined as those with onset after an on-treatment period defined above.

For instances where a patient attends the safety follow-up visit only, but does not attend an earlier IPD visit or EOT visit, adverse events occurring on or after the day of the first dose of study treatment and on or before the last dose of study medication + 28 days will be assigned to the on-treatment period, while AEs with onset date after this time will be assigned to the post-treatment period.

For adolescent data included in the adult completion analyses, only on-treatment AEs will be summarised. AEs will be categorised as having occurred in the on-treatment period if they satisfy one of the following conditions.

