For adult completion analysis, the last dose date for an adolescent is defined as the date of last administered dose on or prior to Week 56.

- For patients who received study treatment at Week 56, AEs in the on-treatment period are defined as those with onset between the date of the first BORA study treatment and the Week 56 visit, inclusively.
- For patients who missed Week 56 visit but continued study after Week 56, AEs with onset on or prior to the last dose date of study treatment (as defined above) + 28 days will be assigned to the on-treatment period.
- For patients who discontinued study treatment prior to Week 56 and had IPD visit, AEs with onset on or prior to the IPD visit date or the last dose date (as defined above) + 28 days + 7 days, whichever is earlier, will be included in the on-treatment period.
- For patients who discontinued study treatment prior to Week 56 and had no IPD visit, AEs with onset on or prior to the date of the last dose of study treatment (as defined above) + 28 days will be assigned to the on-treatment period.

If an AE has a missing onset date then unless the stop date of the AE indicates otherwise, this will be considered an on-treatment event. If an AE has a partial onset date, the handling of partial/missing dates is detailed in Section 8.2.

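### A partial AE start date in the month of first BORA dose is imputed to before dosing, so under the general definitions an AE that began after dosing falls in no AE period

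*SAP*

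**What the plan says.** SAP 8.2 (Appendix B) gives two rules for partial AE start dates: "Missing day of the month: 1st day of the month" and "Missing day and month: Jan. 1st of the year". Neither refers to first dose, to Visit 1 or to the AE end date. The appendix states that these conventions serve to classify on-treatment AEs.

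SAP 3.1.1 sets the periods:

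- **On-study:** "AEs in the on-study period are defined as those with onset between the day of first dose of study treatment" and the scheduled follow-up visit.
- **On-treatment:** also opens on the day of first dose, and closes at EOT or IPD.
- **Post-treatment:** "AEs in the post-treatment period are defined as those with onset after an on-treatment period defined above".

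Section 3.1.1 treats wholly missing and partial onsets differently. For a wholly missing onset, "unless the stop date of the AE indicates otherwise, this will be considered an on-treatment event". For the rest: "If an AE has a partial onset date, the handling of partial/missing dates is detailed in Section 8.2". Section 8.2 in turn places a wholly missing start date at Visit 1, unless the end date is before Visit 1. A wholly missing AE end date gets no imputation: "AE end date will be left as missing".

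Protocol 4.1.1 puts the first BORA dose at Visit 1. Protocol 7.1.3.1 starts BORA AE collection at consent at Visit 1. Protocol 3.5.1 links predecessor AEs into one continuous record.

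**The concern.** An AE newly recorded in BORA cannot, under the protocol's own collection window, have begun before the day of Visit 1. The imputation nevertheless assigns such a date whenever the known month is the first-dose month and dosing was not on the 1st. The event then fits none of the three periods, although its true onset was on-study and on-treatment. An AE about which more is known (the month) is dropped, while one about which nothing is known is kept.

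AEs are a primary endpoint. Protocol 8.5.1.1 and SAP 4.2.5.1 both summarise them by period. The rate in SAP 4.2.5.1 divides patients with the AE by time at risk, so if the dropped event was the patient's only one of that kind, the numerator falls and the denominator does not. The loss is concentrated just after first BORA dose, which for predecessor-placebo patients means their first weeks on benralizumab. At the other end, the same rule pulls day-missing AEs with onset after EOT, but in the EOT month, back into the on-treatment period, which lowers post-treatment counts and rates.

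**Working it through.** The plan states no figure on this point, so there is none to reproduce. The size follows from applying the rules to dates.

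**Example.** First dose 10 March, true onset 20 March, recorded as March with no day. The imputed onset is 1 March, which is before first dose and so in no period. The true date is on-study and on-treatment.

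**Inputs.** From the documents: the imputation rule and the periods above, with scheduled days from SAP Appendix A (adults: EOT Day 393, follow-up Day 477; adolescents: EOT Day 757, follow-up Day 841). Assumed: 365 equally likely first-dose dates (2015), equally likely onset days from first dose to follow-up, completers only, and the same onset rate after EOT. Every percentage below is a share of day-missing AEs with true onset on or after first dose.

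**Lost at first dose.** In a month of L days, the pairs with dosing on day 2 or later and onset from dosing to month end number L(L−1)/2. Over the year: 7 × 465 + 4 × 435 + 378 = 5,373.

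**Gained at EOT.** Day-missing onsets after EOT but in the EOT month move back to the 1st and become on-treatment: 5,397 patient-days in adults (EOT dates run through a leap-year February) and 5,373 in adolescents.

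| Quantity | Adults | Adolescents |
|---|---|---|
| On-study lost | 5,373 / (365 × 477 = 174,105) = 3.1% | 5,373 / (365 × 841 = 306,965) = 1.8% |
| On-treatment lost | 5,373 / (365 × 393 = 143,445) = 3.7% | 5,373 / (365 × 757 = 276,305) = 1.9% |
| On-treatment gained | 5,397 / 143,445 = 3.8% | 5,373 / 276,305 = 1.9% |
| Net on-treatment | +24 / 143,445 = +0.02% | 0 |
| Post-treatment moved to on-treatment | 5,397 / (365 × 84 = 30,660) = 17.6% | 5,373 / 30,660 = 17.5% |

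**First 28 days.** 5,348 / (365 × 28 = 10,220) = 52.3% lost. By week, each out of 365 × 7 = 2,555: 2,219 (86.8%), 1,631 (63.8%), 1,043 (40.8%) and 455 (17.8%).

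**Year-only dates.** With true onset in the calendar year of first dose, 66,430 of 66,795 date pairs (99.5%) fall outside every period. The exception is first dose on 1 January.

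**Scaling to all AEs.** If 1% to 5% of AEs lack the day (assumed range), the loss is 3.1% × 1% to 5% = 0.03% to 0.15% of all adult on-study AEs, and 52.3% × 1% to 5% = 0.5% to 2.6% of AEs in the first 28 days.

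**Sensitivity.** A leap-year start (2016, 366 dates) gives, for adults, 3.1% on-study, 3.8% lost and 3.7% gained on-treatment, and 17.5% post-treatment.

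**The case against.** Six points can be made for leaving the rule alone.

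- **It may rarely bite.** The documents give no count of partial dates. The protocol collects a start date for every AE, schedules Visit 2 at Week 4, has data queried, requires SAE reports within 24 hours of awareness, and observes patients for 2 hours after dosing. Early serious or acute events are the least likely to lack a day. This stands, and it is why the absolute effect is put as small.
- **Some such dates really are pre-dose.** Predecessor AEs are linked into the record, so a month-only date in the first-dose month may be a predecessor onset. If onsets are as frequent per day before dosing as after, the rule misplaces 5,373 / 11,111 = 48.4% of that month's day-missing AEs and places the rest correctly. This stands as a reason to make the floor conditional on where the AE was recorded. It does not justify the rule for AEs newly recorded in BORA.
- **The on-treatment total is nearly balanced now, and a floor unbalances it.** True, but the balance comes from two errors cancelling: early events are dropped and post-EOT events brought in. It does not restore the lost events, and it gives no offset in the on-study period.
- **The protocol governs collection, not imputed analysis dates.** Also true, but for a newly recorded BORA AE the imputed date contradicts the window in which it could have been collected.
- **Some adolescents escape.** In the adult completion analysis, three of the four adolescent rules in SAP 3.1.1 have only an upper limit, for example "AEs with onset on or prior to the last dose date of study treatment (as defined above) + 28 days". Read literally, these keep an AE dated before first dose. The rule for patients dosed at Week 56 and the general definitions do not.
- **Nothing is hidden from medical review.** The listings keep the event. That stands, but the summary tables and rates do not.

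**Conclusion.** The concern holds, as a minor point. Followed exactly, the SAP removes from all general AE periods a day-missing AE that began after first dose in the first-dose month, except when dosing was on the 1st. Year-only dates have the same fault but should be rare.

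The loss is one-way for the on-study period and for the first weeks after dosing. It is not one-way for the on-treatment total, where the EOT shift offsets it. The textual gap is certain; the percentages rest on the assumed uniform dates, completers and constant onset rate, and the share of all AEs affected rests on the assumed 1% to 5%. The study is descriptive and the rule is the same for both regimens, so no biased comparison between regimens is claimed.

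**What to change.** Add to SAP 8.2, for AE start dates only:

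> If the known month and year (or the year alone) match those of the first BORA dose, the AE was newly recorded in BORA, and its end date is missing or not before first dose, set the start date to the first BORA dose date. Otherwise use the 1st of the month or 1 January. AEs linked from the predecessor study keep their predecessor onset.

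State also that a partial date in the month of EOT or IPD counts as on-treatment under the existing rule, and footnote this wherever post-treatment AE rates are reported.

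With the floor, none of the 5,738 enumerated pairs of first-dose date and same-month onset falls outside the periods. The work is one rule, one date comparison, one check of the source record and one footnote.

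There are two drawbacks. A few pre-dose events may be counted as on-treatment. The EOT shift also loses its offset, so day-missing on-treatment AEs are over-counted: 148,842 against a true 143,445 (+3.8%) in adults, and 281,678 against 276,305 (+1.9%) in adolescents. Both are conservative for on-treatment safety. The post-treatment understatement (17.6% and 17.5% of day-missing AEs) is unchanged, which is why the footnote is needed.
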